#### **8.4.3 Prohibited concomitant medications.**

Any treatment that may interfere with the IMP taken during the study. This includes treatment from Day -1/Baseline (Visit 2) until End of Study or Early Termination (except if needed for care and treatment of the subject during the study per Investigator discretion).

The **Error! Reference source not found.** in APPENDIX C provides a listing of prohibited medications; however, it is not a comprehensive list of all restricted medications, supplements, and other therapeutics. Final list with prohibited medications will be identified on a case-by-case basis by a Sponsor medical review of the concomitant medications.

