### 10.7.2 Main analysis

#### 10.7.2.1 Estimand

The primary estimand quantifies the treatment effect of MM-120 at 6-weeks vs placebo after twice weekly administration while accounting for intercurrent events (IEs) with potential confounding effects and IEs leading to study discontinuation prior to the 6-week assessment.

The following attributes describe the primary estimand:

- Population: Subjects in the FAS
- Endpoint: Change from baseline to Week 6 in the AISRS Score
- Treatment of interest: the randomized treatment MM-120 or placebo as a twice weekly treatment.
- Handling of intercurrent events (IEs) prior to AISRS assessments.

Depending on the IE causing the missing or potentially biased value, two sequential policy strategies will be applied:

1. Policy strategy. Available data will be used; missing data will be imputed under a Missing At Random (MAR) assumption by borrowing information from subjects in the same treatment group in following cases:
  - IEs related to COVID-19 pandemic and other intercurrent missing data (see details in Section 10.7.2.1.1).
2. Policy strategy. Available data recorded after the IE will be set to missing; such missing data will be imputed/substituted under a Missing Not At Random (MNAR) assumption by borrowing information from the placebo arm subjects (reference-based imputation) in following cases:
  - Intake of prohibited medications/therapies with potential confounding effect (APPENDIX C) (see details in Section 10.7.2.1.1).
  - Other IEs leading to treatment/study discontinuation (except those related to COVID-19 pandemic (see details in Section 10.7.2.1.1)).

- Summary measure: Difference between MM-120 and placebo in mean change from baseline to Week 6 for AISRS Score.

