#### 10.7.2.1.1 *Definition of intercurrent events (IEs)*

1. IEs related to COVID-19 pandemic are confirmed if:

- AE term AEDECOD is 'SARS-CoV-2 test positive' in the sdtm database. The AE start date AESTDTC will be considered to assign missing values (as defined in bullet 1 of Section 10.7.2.2) to all assessments following this date and up to and including Week 6 D40.

2. Intake of prohibited medications/therapies defined in APPENDIX C will be finalized and flagged accordingly on a case-by-case basis by a Sponsor medical review of the concomitant medications as defined in Section 8.4.3. The CM start date will be considered to assign missing values (as defined in bullet 2 of Section 10.7.2.2) to all assessments following this date and up to and including Week 6 D40.
3. Other IEs leading to treatment/study discontinuation (except those related to COVID- 19 pandemic) are confirmed if:

the action taken AEACNOTH of the corresponding adverse event is 'DRUG DISCONTINUED' or 'SUBJECT WITHDRAWAL' in the sdtm database and subject had study assessments after the AE onset date AESTDTC and up to and including Week 6 D40.

In all cases if the date of the assessment and the IE start date occur in the same date, this assessment values will be assigned to missing.

If the date of assessments following the IE start date are missing, these will be imputed based on the theoretical date the assessments should have been occurred:

- if the IE start date <= study day 9 then both Week 2 and 6 assessments have to be set to missing and imputed
- if the IE start date is between study day 10 and 44 then Week 6 assessment has to be set to missing and imputed

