#### **10.7.2.2 Analysis details**

Primary endpoint, change in AISRS score from baseline to Week 6, will be analyzed applying Rubin's rule to a multiple imputations procedure to appropriate contrasts based on Mixed Model for Repeated Measures (MMRM) analysis of covariance with the change in the AISRS score from baseline to Week 2 and Week 6 visits as dependent variable, and treatment group, visit, visit-by-treatment group interaction, baseline score of AISRS, sex and age as fixed effects. An unstructured variance-covariance matrix will be used to model within-subject errors. Satterthwaite's method will be used to approximate the degrees of freedom. If convergence problems arise (even just in one imputed dataset) the following order of matrices will be applied: Heterogeneous TOEP (TOEPH), Toeplitz (TOEP), Autoregressive(1) (AR(1)). The same variance-covariance matrix will be used in sensitivity analyses.

The imputation model include the longitudinal sequence of AISRS Scores, and the covariates used in the model as defined above. As a general approach, imputations are performed on observed values specifying a minimum and a maximum threshold (zero and 54 respectively) for AISRS. The change from baseline in AISRS Scores will not be imputed to avoid imputation of nonsensical values. For the imputation of missing data of AISRS, one thousand (1000) data sets will be generated, and the random seed number will be 200208. MI will be implemented following the steps below:

1. Imputation assuming a MAR (policy strategy 1).

MAR will be applied following the steps below:

- a)all assessments that took place after the IEs related to COVID-19 pandemic will be kept in the database;
- b)imputing all missing values already present in the data.

MI will be carried out based on fully conditional specification method (FCS, the details will be provided in the 'Programming standards and conventions' document). These datasets will be utilized in Step #2.

2. Imputation assuming MNAR (policy strategy 2).

MNAR will be applied following the steps below:

- a)assigning missing values to all assessments that took place after the IEs specified in policy strategy 2 above;
- b)imputing missing values assigned at step (a).

MNAR assumption based on copy reference approach (i.e. using the non-missing values of the placebo arm) will be used.

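### The SAP's same-date rule can delete a pre-dose AISRS rating that came before the intercurrent event, mainly at Week 2 and more rarely at Week 6

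*SAP*

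**What the plan says.** - **Estimand (SAP 10.7.2.1).** The attribute is titled "Handling of intercurrent events (IEs) prior to AISRS assessments". Under the second policy strategy, "Available data recorded after the IE will be set to missing". Step 2a of SAP 10.7.2.2 agrees: "assigning missing values to all assessments that took place after the IEs specified in policy strategy 2 above". Protocol 13.6.1 uses the same ordering.
- **Replacement (SAP 10.7.2.2).** "MNAR assumption based on copy reference approach (i.e. using the non-missing values of the placebo arm) will be used".
- **Working rule (SAP 10.7.2.1.1).** For every type of event, "if the date of the assessment and the IE start date occur in the same date, this assessment values will be assigned to missing".
- **Triggers (SAP 10.7.2.1.1).** An adverse event counts if it led to stopping the drug or to withdrawal and the "subject had study assessments after the AE onset date AESTDTC and up to and including Week 6 D40". For medications, "The CM start date will be considered to assign missing values", once the Sponsor's case-by-case review has flagged the drug. SAP 8.4.3 applies the prohibition "except if needed for care and treatment of the subject during the study per Investigator discretion".
- **Timing of ratings.** Protocol 6.2.4.1 places the Week 2 AISRS before the third dose (nominal Day 8). Protocol 6.2.4.4 lists the Week 6 AISRS among the activities before the last dose (nominal Day 40). SAP 8.9.1 defines the key secondary endpoint as the pre-dose value after two doses.
- **Clock times.** SAP 2.1.2 says that assessment times are recorded. Layout L18 (AISRS) and Layout L10 (adverse events) both carry a time. Layout L6 (medications) shows start and stop dates only, but it links a medication to the adverse event it treated.

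**The concern.** On a visit where the protocol is followed, the order is rating, dose, then any reaction to that dose. Protocol 1.4.3 puts the onset of subjective effects at 20 µg at about 0.7 h after dosing. A qualifying event on that day that is a reaction to the dose, or a medication given for such a reaction, therefore comes after the rating. The estimand would keep the rating. The same-date sentence removes it, and strategy 2 then fills the gap from placebo data. Appendix D of the SAP does not list this widening among its changes to the protocol's analyses.

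What is at stake is an observed, valid value of the key secondary or, less often, the primary endpoint. Reactions to the dose are more likely on MM-120 (an inference), so the losses would fall mainly in that arm and pull its mean toward placebo. That shrinks a true benefit and would also mask a true worsening. A rating lost in the placebo arm costs information but causes no systematic shift, because its replacement comes from its own arm.

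**Working it through.** **1. Which ratings the rule can reach**

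| Event starting after the rating, same day | Week 2 visit (Day 8) | Week 6 visit (Day 40) |
|---|---|---|
| Adverse event leading to discontinuation or withdrawal | Deleted, if a later assessment exists up to Day 40 | Not reached: no assessment can follow the onset date and still fall by Day 40 |
| Sponsor-flagged prohibited medication | Deleted | Deleted (primary value) |

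COVID-19 events lie outside this point. Step 1a of SAP 10.7.2.2 keeps the data recorded after them, and their missing values are imputed within arm under MAR.

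**2. The plan's own figure.** Inputs from Protocol 13.6.4: 26 per arm, standardized effect 0.60, one-sided 0.10. Power = Φ(0.60 × √(26/2) − 1.282) = Φ(2.163 − 1.282) = 0.811. With the noncentral t distribution on 50 df it is 0.806. The stated 80% reproduces.

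**3. Upper bound per replaced MM-120 Week 6 rating.** One rating is 1/26 = 3.8% of the arm. If it is replaced by a value centred on the placebo mean, the estimate moves by 0.60/26 = 0.023 SD toward zero. The standard error of the difference is about √(2/26) = 0.277 SD, so the shift is 0.023/0.277 = 8% of one standard error. As an illustration with SD and N unchanged, the effect falls from 0.600 to 0.577 and power (noncentral t) from 80.6% to 78.3%.

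**4. When the subject's own Week 2 rating informs the imputation.** Let d2 be the true Week 2 difference and ρ the Week 2 to Week 6 correlation. The documents give neither; take ρ = 0.6 and d2 between 0 and 0.6 SD. The shift is (0.60 − ρ·d2)/26:
- d2 = 0: 0.60/26 = 0.023 SD
- d2 = 0.3: 0.42/26 = 0.016 SD
- d2 = 0.6: 0.24/26 = 0.009 SD

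**5. A Week 2 rating deleted through the adverse-event route.** The shift in the key secondary estimate is d2/26: 0, 0.012 or 0.023 SD for d2 = 0, 0.3 or 0.6. The intended strategy already treats this subject's Week 6 value as missing, so that loss is not due to the same-date rule. What the rule adds at Week 6 is the loss of the Week 2 rating as a predictor, worth ρ·d2/26: 0, 0.007 or 0.014 SD.

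**6. Frequency.** Neither document gives a rate of discontinuations or flagged medications with onset on a dosing day, so no expected number of deletions can be derived.

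**7. Planned analyses that keep the rating.** The tipping-point and copy-reference analyses (SAP 10.7.3.1, 10.7.3.2) re-impute the deleted values. The per-protocol and severity analyses (10.7.3.4, 10.7.3.5) rerun the main analysis. Only the complete-case analysis (10.7.3.3) keeps the rating, and it drops all the policy strategies at once, so it does not isolate this rule.

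**The case against.** The case for leaving the text alone is substantial. A tie rule at date level is a common convention, and medication start times do not appear in Layout L6. The routes are narrow. Ordinary reactions do not qualify, because the adverse event must end in discontinuation or withdrawal. For medications, Appendix C allows only benzodiazepines during the study, for anxiety, and SAP 8.4.3 may exempt treatment needed for care. The Sponsor's review could also decline to flag a drug taken after the rating, since it cannot have confounded that rating. Protocol 7.2.1 does not expect pronounced anxiety at this dose. The shift is under a tenth of a standard error and, under a true benefit, conservative. Observed values also appear in the AISRS listing and should appear in the descriptive change table (SAP 12.4.4.2).

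All of this limits the size of the problem, and it stands. It does not remove the mismatch: the sentence discards ratings that the estimand keeps, and for adverse events the times needed to order them correctly are already collected. Conservative for a benefit claim is also not neutral, since a harm would be diluted in the same way.

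Three stronger readings are tempting, but the documents do not support them:
- A reader might infer that any reaction later the same day deletes the rating, or that a reaction to the final dose deletes the primary value. The conditions on adverse events rule out both.
- A reader might infer that SAP 10.12.1.1 contradicts the rule, because it counts a same-day adverse event with missing time as after dosing. That section orders an event against a dose for a safety table, whereas the present rule orders a rating against an event.
- A reader might want to state a probability of loss or an overall power loss. That needs an event rate that the documents do not give.

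**Conclusion.** The point holds in limited form. The same-date sentence goes beyond the estimand and can replace a valid earlier rating with placebo-based values. The clearer case is the Week 2 key secondary rating, lost through an adverse event after the Day 8 dose that leads to discontinuation or withdrawal. The less likely case is a flagged medication first taken after the rating on Day 8 or Day 40; only this route reaches the primary value.

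The size is at most 0.023 SD toward placebo per replaced MM-120 Week 6 rating, about 8% of one standard error. This assumes a true effect of 0.60 SD, 26 per arm, and a subject whose expected response equals the arm mean. The number of such subjects is unknown. Priority: low to moderate.

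**What to change.** In SAP 10.7.2.1.1, replace the same-date sentence with: *An AISRS assessed on the IE start date is set to missing only if its date/time is on or after the IE start date/time.* Then add:

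- If the adverse event's onset time is missing, keep a rating timed before that day's dose.
- For a medication, which is listed with a start date only, keep the rating if the medication is linked to an adverse event that began after the rating. Otherwise keep the present rule.
- Report by arm how many same-date ratings were set to missing.

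This needs a few sentences in the SAP, slightly more programming and one count in the output. It needs no new data, visits or staff. The rule becomes slightly less conservative, and a same-day medication with no linked adverse event will still delete the rating. The count by arm will show whether any of this occurred.

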#### **10.7.2.2 Analysis details**

Primary endpoint, change in AISRS score from baseline to Week 6, will be analyzed applying Rubin's rule to a multiple imputations procedure to appropriate contrasts based on Mixed Model for Repeated Measures (MMRM) analysis of covariance with the change in the AISRS score from baseline to Week 2 and Week 6 visits as dependent variable, and treatment group, visit, visit-by-treatment group interaction, baseline score of AISRS, sex and age as fixed effects. An unstructured variance-covariance matrix will be used to model within-subject errors. Satterthwaite's method will be used to approximate the degrees of freedom. If convergence problems arise (even just in one imputed dataset) the following order of matrices will be applied: Heterogeneous TOEP (TOEPH), Toeplitz (TOEP), Autoregressive(1) (AR(1)). The same variance-covariance matrix will be used in sensitivity analyses.

The imputation model include the longitudinal sequence of AISRS Scores, and the covariates used in the model as defined above. As a general approach, imputations are performed on observed values specifying a minimum and a maximum threshold (zero and 54 respectively) for AISRS. The change from baseline in AISRS Scores will not be imputed to avoid imputation of nonsensical values. For the imputation of missing data of AISRS, one thousand (1000) data sets will be generated, and the random seed number will be 200208. MI will be implemented following the steps below:

1. Imputation assuming a MAR (policy strategy 1).

MAR will be applied following the steps below:

- a)all assessments that took place after the IEs related to COVID-19 pandemic will be kept in the database;
- b)imputing all missing values already present in the data.

MI will be carried out based on fully conditional specification method (FCS, the details will be provided in the 'Programming standards and conventions' document). These datasets will be utilized in Step #2.

2. Imputation assuming MNAR (policy strategy 2).

MNAR will be applied following the steps below:

- a)assigning missing values to all assessments that took place after the IEs specified in policy strategy 2 above;
- b)imputing missing values assigned at step (a).

MNAR assumption based on copy reference approach (i.e. using the non-missing values of the placebo arm) will be used.

3. The MMRM model defined above will be run on each of the 1000 generated datasets with observed and imputed data. Rubin's rule will be used for combining results to draw inference.

In the evaluation of the primary endpoint will be included only subjects with NON missing baseline assessments.

The LS Means along with associated standard errors (SE) and 95%CIs will be displayed for each treatment group at each time point. For the comparison of MM-120 vs placebo treatment effect, the LS Mean, SE, 95%CI and one-sided p-value will be provided.

A listing of AISRS values overtime will be provided for the FAS population.

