3. STUDY PLAN AND PROCEDURES

3.1 Overall Study Design

This study is a multi-center, randomized, double-blind, placebo-controlled Phase 2a study of low dose MM-120 (20 µg) compared with a placebo administered for 6 weeks (twice a week).

There will be a 1:1 randomization, double-blind, to MM-120 or placebo of 52 adults with ADHD with the aim to reach 26 evaluable subjects in each of the 2 arms at Week 6.

There will be 2 arms:

- Arm 1-Placebo: a total of 26 subjects will receive a placebo identical in appearance to the IMP administered orally twice weekly for 6 weeks. Subjects and site staff will remain blinded to the treatment arm.
- Arm 2-MM-120: a total of 26 subjects will receive 20 µg of MM-120 twice weekly for 6 weeks. Subjects and site staff will remain blinded to the treatment arm.

Subjects will be evaluated at Baseline, Week 1, Week 6, and Week 10 (follow-up) for AISRS and CGIS by a trained study personnel; the primary endpoint will be based on evaluation of AISRS at Baseline and at Week 6, with a key secondary endpoint after 1 week of treatment.

Subjects are free to discontinue the study at any time without providing a reason. However, the Investigator should try to identify the reason and document in the eCRF.

Specific reasons for discontinuing from the study should be documented in the eCRF, and include, but are not limited to:

- Subject's decision
- The Investigator or Sponsor judges that it is in the best interest of the subject to stop study treatment due to any abnormality compromising subject safety
- Pregnancy
- Severe noncompliance to the study protocol as judged by the Investigator and/or the Sponsor.

Subjects who prematurely discontinue may be replaced, per Sponsor decision. Subjects will not be allowed to re-enter the study.

The study will stop enrolling subjects once 26 subjects per arm are randomized, or if the Investigator or the Sponsor judges that it is in the best interest of the subjects to stop study enrollment due to low accrual or safety or other reason. Subjects who have given informed consent and have not yet been excluded, completed, or terminated from the study will be allowed to continue in the study. An evaluable subject is defined as a randomized subject (as defined in the Statistical Analysis Plan [SAP]).

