6.2.6. ADHD assessments

6.2.6.1 Adult ADHD Investigator Symptom Rating Scale

The Adult ADHD Investigator Symptom Rating Scale (AISRS) is a clinician-administered scale that assesses each of the DSM-5 symptoms of ADHD. The AISRS not only uses the adult ADHD prompts from the Adult ADHD Clinical Diagnostic Scale (ACDS) v1.2, but each of the stem questions are designed to better capture symptoms of the disorder as they present in adulthood. It has been used and validated many times in a variety of clinical drug trials.

The AISRS total score consists of 18 items from the original ADHD-RS, which were derived based on DSM- 5 criteria for ADHD. The ADHD-RS includes 9 items that address symptoms of inattention, and 9 items that address symptoms of impulsivity and hyperactivity. Each item is rated from 0 to 3. The AISRS total score can range from 0 to 54. A higher score corresponds to a worse severity of ADHD.

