6.2.8.2 Discounting task

In the delay discounting task subjects are presented 114 questions. For each question, subjects have to indicate which of two hypothetical rewards they prefer, the ‘standard’ or the ‘alternative’ item. The standard item, 100 Swiss francs, is available after one of five delays (0, 7, 30, 180, or 365 days). The alternative item is an amount of money (1, 25, 50, 100, 150, 200, 250, 300, 350, 400, 450, 500, 550, 600, 650, 700, 750, 800, 850, 900, 950, 1000, or 1050 Euros (Maastricht site)/Swiss francs (Basel site) available after 0 days). Each combination of standard and alternative item is only used once and presented in random order. Subjects are asked to

express their preference for an item by pressing one of two buttons. Recorded response choices are used afterwards to calculate the switch points per delay at which the subject preferred the alternative item over the standard item. Task duration is 10 minutes. Previous research demonstrates excessive delays discounting among individuals with ADHD (Kuypers et al., 2007; Mitchell, 1999).

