13.6.2. Statistical methods and analysis

The primary analysis will be performed according to the intent-to-treat (ITT) principle on the FAS.

The effect on the primary endpoint, change in AISRS score from baseline to Week 6, will be estimated by applying Rubin's rule to a multiple imputations procedure to appropriate contrasts based on Mixed Model for Repeated Measures (MMRM) analysis of covariance with the change from baseline in the AISRS score at all visits following randomization as dependent variable, and treatment group, visit, visit-by-treatment group interaction, baseline score of AISRS, sex and age as fixed effects. An unstructured variance-covariance matrix will be used to model the within-subject errors and Satterthwaite's method will be used to approximate the degrees of freedom. The SAP will describe alternatives in case of non-convergence obtained by analyzing any multiply imputed idem.

Sensitivity analyses will be performed as follows:

- Assuming that subjects on active treatment with any missing data follows the distribution of the placebo responses.
- Assuming that subjects on active treatment with any missing data perform worse than MAR by a penalty.

The details of the primary and sensitivity analysis methods will be specified in the SAP.

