### 10.8.1 Key Secondary Endpoint

#### 10.8.1.1 *Change from baseline in AISRS at Week 2*

The change from baseline (see Section 8.1.2) to Week 2 in AISRS Score will be analyzed using the same estimand and imputation process as the primary endpoint. The linear mixed effects model analysis of covariance (ANCOVA) with the change from baseline in the AISRS score at Week 2 following randomization as dependent variable, and treatment group, baseline score of AISRS, sex and age as fixed effects will be used in current analysis. The outcome will be considered confirmatory, if in agreement with the primary endpoint outcome and provided that the null hypothesis is rejected for the primary outcome. This gatekeeping function of the primary outcome allows to avoid any adjustment for multiplicity of testing.

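### The efficacy models in this multi-site, clinician-rated trial carry no site or country term: a valid analysis that gives up some precision cheaply recovered

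*SAP*

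**What the plan says.** Protocol 3.1 describes the design: "This study is a multi-center, randomized, double-blind, placebo-controlled Phase 2a study". The site list in the synopsis is redacted, but Protocol 6.2.8.2 names a Maastricht and a Basel site. Protocol 6.2.6.1 says of the AISRS that it "is a clinician-administered scale that assesses each of the DSM-5 symptoms of ADHD".

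The covariates in the efficacy models are:

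- **Primary MMRM, SAP 10.7.2.2:** "treatment group, visit, visit-by-treatment group interaction, baseline score of AISRS, sex and age as fixed effects". Protocol 13.6.2 gives the same list.
- **Imputation, SAP 10.7.2.2:** "The imputation model include the longitudinal sequence of AISRS Scores, and the covariates used in the model as defined above".
- **Key secondary ANCOVA, SAP 10.8.1.1:** "treatment group, baseline score of AISRS, sex and age as fixed effects will be used in current analysis".

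SAP 10.7.3 lists five sensitivity analyses. The only stratified one uses baseline ADHD severity. Country is collected as a demographic variable (SAP 8.1.1), and Protocol 13.3 plans a baseline summary by geographical region, but neither enters an efficacy model. Protocol 5.1 describes a code produced by the study biostatistician and mentions no stratification or blocking. No reason is given for leaving site out, and SAP Appendix D does not mention it.

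**The concern.** Sites can differ in how much patients change on a clinician-rated scale, even at equal baseline scores. One source specific to this trial is that visits after Day 1 may be held remotely at the investigator's discretion, with site space among the listed reasons (Protocol 6.2.4). Rating conditions may therefore diverge between sites after baseline, where the baseline score cannot correct for it.

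Without a site term, any such difference stays in the residual variance. With 26 per arm, an uneven split of sites between arms can also move the one estimate the trial produces, and no planned analysis would show by how much. At stake are precision and readability of the result, not the validity of the test.

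**Working it through.** **Inputs from the documents** (Protocol 13.6.4): 26 per arm, standardized difference 0.60, one-sided alpha 0.10, 80% power.

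**Assumptions, not in the documents:** two sites of equal size; a between-site difference s in mean change given baseline of 0, 0.3, 0.5 or 0.8 SD; 0.60 standardized on the total SD.

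**1. The plan's own figure.** Noncentrality = 0.60 × √(26/2) = 2.163. With 50 df and a critical t of 1.299, power is 0.806. The stated 80% is reproduced without a site term.

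**2. Power with site added.** Two equal sites a distance s apart account for s²/4 of the total variance. Removing that share gives an adjusted effect of 0.60/√(1 − s²/4), tested on 49 df.

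| s (SD) | Site share s²/4 | Adjusted effect | Power |
|---|---|---|---|
| 0 | 0 | 0.600 | 80.6% |
| 0.3 | 0.0225 | 0.607 | 81.3% |
| 0.5 | 0.0625 | 0.620 | 82.5% |
| 0.8 | 0.16 | 0.655 | 85.5% |

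**3. More sites.** Starting from 47 df for a model with baseline, sex and age, and varying the number of sites from 2 to 6, power with site added is 0.805–0.806 for a site share of 0, 0.820–0.821 for 0.05 and about 0.836 for 0.10. The extra degrees of freedom cost almost nothing.

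**4. Chance imbalance under an unstratified list.** The between-arm difference in site share has SD √(2 × 0.25/26) = 0.139. At s = 0.5 this adds an error with SD 0.5 × 0.139 = 0.069, or variance 0.0048. The sampling variance of the treatment difference is 2/26 = 0.0769, and 0.0048/0.0769 = 6.25%. That is the same 6.25% as the site share in step 2, so this error is already inside the unadjusted standard error.

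**5. What one trial could show.** With two sites of 26, the 95th percentile of the absolute imbalance in site share is 8/26 = 0.31. At s = 0.3, 0.5 or 0.8 this moves the estimate by 0.09, 0.15 or 0.25 SD, against a design effect of 0.60.

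**6. Type I error.** In a simulation of two sites of 26 (10,000 runs per setting, site difference and effect in within-site SD units), the model without site rejects a true null as follows:

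| Site difference | Unstratified list | List balanced within site |
|---|---|---|
| 0.3 | 0.098 | 0.092 |
| 0.5 | 0.101 | 0.090 |
| 0.8 | 0.099 | 0.086 |

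The Monte Carlo standard error is √(0.1 × 0.9/10,000) = 0.003. The test holds its level under an unstratified list and is somewhat conservative under a balanced one.

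**7. The other reading of 0.60.** If 0.60 is in within-site SD units, simulated power under an unstratified list, without and with site, is 0.80/0.80, 0.79/0.80 and 0.76/0.80 for the three differences. On that reading, adjustment restores the planned power and does not exceed it.

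**The case against.** Protocol and SAP agree on the covariates, no documented stratification factor has been left out, and the test is valid as planned. The gain is under 2 points of power unless the site difference is large, and neither the size of that difference nor the number of sites is known. All of this stands. It limits the point to efficiency and transparency.

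Three stronger readings are tempting, and the documents do not support them.

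- **Bias or a false-positive risk.** Randomized allocation excludes average bias, and step 6 shows no inflation.
- **Two separate losses.** Step 4 shows that, under an unstratified list, chance imbalance and unexplained site variance are one quantity. If the list was balanced within site, imbalance largely disappears and only an overlarge standard error remains.
- **Harsher or more lenient raters distort the comparison.** The outcome is change from baseline with baseline AISRS as a covariate, so a stable difference in rating level is largely absorbed. The documents also do not say that each site had its own raters.

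Timing is the most practical objection. SAP Appendix B says that version 2.0 was issued for the clinical study report. It changed one pharmacodynamic display because nearly all medians were zero, so at least some data had been looked at. Whether treatment codes were open is not stated. Changing the primary model after unblinding would invite the charge of data-driven choice, and Protocol 13.1 requires the SAP to be final before then. The fix has to allow for this.

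**Conclusion.** The omission is real and runs through the MMRM, the imputation model, the Week 2 ANCOVA and every listed sensitivity analysis. The planned test remains valid without site. Under the assumptions in the working, adjustment is worth 0.7, 1.9 or 4.9 points of power at site differences of 0.3, 0.5 or 0.8 SD, and nothing if sites do not differ. It would also show how far the realised estimate depends on the split of sites between arms. This is a cheap improvement, not a defect that threatens the conclusion.

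**What to change.** If treatment codes were still closed at SAP 2.0, add site as a fixed effect to the MMRM and imputation model in SAP 10.7.2.2, the ANCOVA in 10.8.1.1 and the sensitivity analyses in 10.7.3. If sites are many or small, use country, or pool small sites by a rule fixed before unblinding. Small sites need this most in the copy-reference imputation, which draws on at most 26 placebo subjects, and in the severity-stratified fits. Record the change in Appendix D, and state there whether the randomization list was balanced within site.

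If treatment codes were already open, leave the prespecified primary model alone and report the site-adjusted model as one labelled sensitivity analysis.

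The cost is S − 1 degrees of freedom for S sites (1 with two sites), a pooling rule and some SAP wording. No new data are needed.
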